## 1.2 Rationale for study design, doses and control groups

This two-part study will allow the impact of orally-dosed osimertinib on the PK of fexofenadine to be characterised, and will provide information on the potential DDI between fexofenadine and osimertinib:

- The PK phase will assess the effect of osimertinib on the PK parameters of fexofenadine following both single and multiple oral dosing of osimertinib.
- Continued access will allow patients who have completed the PK phase to receive a therapeutic dose of osimertinib on a continuous basis and therefore possibly gain clinical benefit.

A sequential design has been chosen for the PK phase as a substantial washout between treatments would be required in a randomised cross-over design which is not medically appropriate for the patient population participating in this study.

The rationale for the doses of study treatments chosen are as follows:

- Osimertinib 80 mg once daily will deliver exposure that has been previously demonstrated to be acceptable and tolerated in patients with cancer, and is the dose approved for use in this patient population.
- Fexofenadine hydrochloride 120 mg once daily is a typical dose used clinically and has previously been utilised in DDI studies.

The initial comparison of single dose fexofenadine data obtained on Day 1 of Treatment Period 2, when given with a single dose of osimertinib, will exclusively assess the potential of osimertinib to inhibit P-gp. Osimertinib will be subsequently dosed to steady state in order to determine its overall impact on a change in P-gp activity, if any, as inducer or inhibitor of P-gp. Osimertinib and its metabolites reach steady-state in plasma by 21 days of dosing. An additional 10-11 days of dosing will ensure that the PXR activated P-gp enzymes reach steady state. Hence, a minimum of 32 days of osimertinib dosing is utilized in this study. Fexofenadine exhibits linear pharmacokinetics. A single dose of fexofenadine given under each of the 2 concomitant osimertinib conditions compared to a single dose of fexofenadine given alone should be sufficient to evaluate a potential inhibitory effect of osimertinib on P-gp (Day 1 of Treatment Period 2) and potential induction of P-gp by osimertinib (Day 39, Treatment Period 2), if any.

Patients with cancer are required for this study because pre-clinical toxicology data preclude the use of osimertinib in healthy volunteers with multiple dosing. This study requires osimertinib to be at steady state to maximise the likelihood of seeing an effect on fexofenadine PK.

Safety and tolerability data will be collected as per regulatory and ethical guidelines and will expand the safety/tolerability database for patients with EGFRm+ NSCLC treated with oral osimertinib tablets.

### **1.3 Benefit/risk and ethical assessment**

This study is robustly designed to assess the primary objective while minimising the number of patients exposed to osimertinib. Osimertinib demonstrates acceptable benefit-risk profile in patients with NSCLC as evidenced by its approval from the regulatory agencies in US, EU, Japan, Israel and South Korea. Clinical tolerability data from patients indicate that osimertinib is generally well tolerated by patients with advanced cancer (please refer to Section 1.3 of the IB for details). Importantly, data from a Phase I study (D5160C00001) in this patient population has demonstrated osimertinib to be well tolerated, with good evidence of efficacy. All studies of osimertinib exclude patients with clinically significant toxicities related to prior treatments in addition to specifically excluding patients with a history of interstitial lung disease (ILD) or clinically active ILD as this is an uncommon but well documented EGFR related toxicity. All patients are assessed for known EGFR related toxicities and detailed information on the management of toxicities related to investigational product (IP) is provided for all osimertinib studies (Section 6.7). Possible side-effects of using fexofenadine include, but are not limited to: headache, drowsiness, dizziness, nausea, fatigue, hypersensitivity reactions (with manifestations such as angioedema, chest tightness, dyspnoea, flushing and systemic anaphylaxis), insomnia, nervousness, sleep disorders or nightmares/excessive dreaming (paroniria), tachycardia, palpitations, diarrhoea, rash, urticarial and pruritus.

All adverse events (AEs), vital signs, electrocardiograms (ECGs) and laboratory data will be collected and reviewed by the clinical study team on an ongoing basis.

Although patients may not benefit from fexofenadine, there may be some benefit gained from osimertinib. Further benefit may be gained during continued access. If the Investigator believes it is in the patient's interest, the patient may continue treatment with osimertinib until such time as the Investigator believes they are no longer deriving clinical benefit or they stop taking osimertinib for any other reason.

In addition to the potential effect on P-glycoprotein (P-gp), clinical studies indicate that osimertinib inhibits the breast cancer resistance protein (BCRP) transporter. Also, exposure of osimertinib is decreased when co-administered with strong CYP3A inducers. Measures have been taken in this protocol to provide appropriate restrictions and/or direction for use of concomitant medications which are substrates for these metabolising enzymes or transporters.

The data generated from this study will support labeling of osimertinib for appropriate use in patients with NSCLC. The overall risk for the patients who participate in this study to assess how co-administration of osimertinib affects the PK of fexofenadine is acceptable.

## 1.4 Study Design

This is a Phase I, open-label, non-randomised, two-part study in patients with EGFRm+ NSCLC who have progressed on an EGFR-TKI.

The PK phase will assess the effect of osimertinib on the PK parameters of fexofenadine following both single and multiple oral dosing of osimertinib.

Continued access will provide patients with further access to osimertinib after the PK phase.

The study will be conducted at approximately 10 sites across Asia and Western Europe, with approximately 24 patients enrolled in order to achieve at least 18 evaluable patients. Additional patients may be dosed to ensure the minimum number of evaluable patients. For full details of the study plan and timing of procedures, see Section 4.

### PK phase

[figure not shown]
The PK phase is a non-randomised, open-label, 2-period design. Treatment Period 1 and Treatment Period 2 are separated by a 3 to 7 day washout period between doses. A study flow chart for the PK phase is presented in [Figure 1](#). Patients will receive osimertinib 80 mg as a single dose on Day 1 of Treatment Period 2, then 80 mg once daily for 38 days (from Day 4 to Day 41 in Treatment Period 2). Patients will also receive a single oral dose of fexofenadine on Day 1 in Treatment Period 1, and on Days 1 and 39 in Treatment Period 2.

### Continued access

On completion of the PK phase (ie, following collection of the 72-hour fexofenadine sample on Day 42), patients may continue to take osimertinib tablets (80 mg once daily) as a single agent in continued access if they and the Investigator agree that this is appropriate. This will continue until the Investigator believes they are no longer deriving clinical benefit, or they stop taking osimertinib for any other reason. No clinical data will be collected during this phase other than sudden death of unknown reason, serious adverse events (SAEs) that may be related to osimertinib, outcomes of pregnancy and drug dispensing/accountability.

If a patient discontinues treatment during the PK phase, they will return to the clinic for follow-up assessments 30 days ( $\pm 7$  days) after their last dose of treatment in the PK phase. If the patient's last dose of osimertinib is in continued access, the patient should be contacted 30 days after their last dose of osimertinib to follow-up any existing SAEs, monitor for new SAEs that may be related to the IP, and record any sudden deaths of unknown cause.

**Figure 1 Study flow chart**

- a Visit 7 procedures may start on the day of Visit 6 or up to 4 days after Visit 6.  
b Blood samples will be collected for 72 hours after fexofenadine administration.  
c Treatment may commence immediately after the 72 hour blood collection on Day 4 of Treatment Period 1, or an interval of up to 3 additional days may be included; the washout may not exceed 7 days between fexofenadine doses. In Treatment Period 2, from Day 4 (after the 72 hour blood collection, if applicable) until Day 41, patients will receive a daily dose of osimertinib 80 mg.  
d Osimertinib dosing starts on Day 4 after collection of the 72-hour blood samples.  
e Osimertinib 80 mg plus fexofenadine hydrochloride 120 mg administered together on Day 39, followed by osimertinib for 2 additional days. Final fexofenadine blood sample will be collected at 72 hours (on Day 42).  
f For patients who withdraw from the study prematurely and do not go onto continued access.

EGFR epidermal growth factor receptor; EGFRm+ Activating mutations in EGFR; EGFR-TKI EGFR-tyrosine kinase inhibitor(s)

## 2. STUDY OBJECTIVES

### 2.1 Primary objective

| Primary Objective:   | Outcome Measure:   |
|--|--|
| To investigate the effect of osimertinib on the AUC and $C_{max}$ of fexofenadine (a sensitive P-gp substrate) after both single and multiple osimertinib dosing | Fexofenadine AUC and $C_{max}$ (alone and in combination with osimertinib) |

AUC area under the plasma concentration time curve from zero to infinity;  $C_{max}$  maximum plasma concentration; P-gp P-glycoprotein.

### 2.2 Secondary objectives

| Secondary Objective:   | Outcome Measure :  |
|--|--|
| To assess fexofenadine $AUC_{(0-t)}$ , $t_{1/2\lambda z}$ , $t_{max}$ , CL/F and $V_z/F$ in patients for fexofenadine administered alone and in combination with osimertinib | Fexofenadine $t_{max}$ , $AUC_{0-t}$ , CL/F, $V_z/F$ , $\lambda_z$ , $t_{1/2\lambda z}$ (alone and in combination with osimertinib)  |
| To assess the PK of osimertinib and metabolites in combination with fexofenadine   | Osimertinib and metabolites (AZ5104 and AZ7550):
Single dose: $AUC_{0-72}$ , $C_{max}$ , $t_{max}$ , and the metabolite ratio (AZ5104:osimertinib, AZ7550:osimertinib) $MRC_{max}$ .
Multiple dose: $AUC_{\tau}$ , $C_{ss,max}$ , $t_{ss,max}$ , $C_{ss,min}$ and $CL_{ss}/F$ (osimertinib only). In addition, the metabolite ratios (AZ5104:osimertinib, AZ7550:osimertinib) $MRAUC_{\tau}$ and $MRC_{ss,max}$ .
Trough concentrations on D11, D18, D25, and D32 for osimertinib and metabolites |

AZ5104 and AZ7550 are metabolites of osimertinib

AUC area under the plasma concentration-time curve from zero extrapolated to infinity;  $AUC_{0-72}$  area under plasma concentration-time from time zero to 72 hours post-dose;  $AUC_{0-t}$  area under plasma concentration-time from time zero to the last quantifiable concentration;  $AUC_{\tau}$  area under plasma concentration-time from time zero to the end of the dosing interval; CL/F apparent plasma clearance following oral administration;  $CL_{ss}/F$  apparent plasma clearance at steady state;  $C_{max}$  maximum plasma concentration;  $C_{ss,max}$  maximum plasma concentration at steady state;  $C_{ss,min}$  minimum plasma concentration over the dosing interval;  $MRAUC_{\tau}$  metabolite-parent ratio of  $AUC_{\tau}$ ;  $MRC_{max}$  metabolite-parent ratio of  $C_{max}$ ;  $MRC_{ss,max}$  metabolite-parent ratio of  $C_{ss,max}$ ;  $\lambda_z$  terminal rate constant;  $t_{1/2\lambda z}$  terminal half-life;  $t_{max}$  time to  $C_{max}$ ;  $t_{ss,max}$  time to  $C_{ss,max}$ ;  $V_z/F$  apparent volume of distribution.

## 2.3 Safety objectives

| Safety Objective:  | Outcome Measure :   |
|--|---|
| To investigate the safety and tolerability of osimertinib when administered in combination with fexofenadine in NSCLC patients | AEs/SAEs graded by CTCAE (Version 4)

Vital signs (blood pressure /pulse/temperature/height/weight)

Laboratory parameters (clinical chemistry/haematology/urinalysis)

Physical examination

Standard 12-lead ECGs

Ophthalmology

Echocardiogram/multiple gated acquisition scan (MUGA) |

## 2.4 Exploratory objectives

| Exploratory Objective:  | Outcome Measure :   |
|---|---|
| To provide data to allow analysis using population PK approaches  | Population PK analyses for C max , AUC and other PK parameters as appropriate. Population PK analyses, if conducted, will be reported separately from the CSR. |
| To collect optional plasma samples for deoxyribonucleic acid (DNA) extraction and storage to enable an investigation into the impact of host polymorphisms of (ADME)-related genes on the absorption, distribution, metabolism and excretion of osimertinib |   |

## 3. SUBJECT SELECTION, ENROLMENT, RANDOMISATION, RESTRICTIONS, DISCONTINUATION AND WITHDRAWAL

Each patient should meet all of the inclusion criteria and none of the exclusion criteria for this study. Under no circumstances can there be exceptions to this rule.

### 3.1 Inclusion criteria

For inclusion in the study patients should fulfil the following criteria:

1. Provision of signed and dated, written informed consent prior to any study specific procedures, sampling and analyses. Procedures performed for routine clinical practice up to 2 weeks before the provision of written consent are acceptable if not intentionally done for study purposes.
2. Male or female, aged  $\geq 18$  years
3. Histological or cytological confirmation diagnosis of NSCLC
4. Radiological documentation of disease progression while receiving previous continuous treatment with an EGFR-TKI eg, afatinib, gefitinib or erlotinib. In addition, other lines of therapy may have been given. All patients must have documented radiological progression on the last treatment administered prior to enrolling in the study.
5. Confirmation that the tumour harbours an EGFR mutation known to be associated with EGFR-TKI sensitivity (eg, G719X, exon 19 deletion, L858R, L861Q).
6. Eastern Cooperative Oncology Group (ECOG) performance status 0 to 1, with no deterioration over the previous 2 weeks.
7. Patients must have a life expectancy of  $\geq 12$  weeks, as estimated at the time of screening.
8. Females should be using adequate contraceptive measures (see [Appendix E](#)) and must have a negative serum pregnancy test prior to start of dosing if of child-bearing potential or must have evidence of non-child bearing potential by fulfilling one of the following criteria at screening (see details in [Appendix E](#)):
  - Post-menopausal, defined as aged  $\geq 50$  years and amenorrhoeic for at least 12 months following cessation of all exogenous hormonal treatments
  - Women  $< 50$  years old who are considered as post-menopausal (amenorrhoeic for 12 months or more following cessation of all exogenous hormonal treatments) and who have luteinizing hormone (LH) and follicle-stimulating hormone (FSH) levels in the post-menopausal range for the institution
  - Documentation of irreversible surgical sterilisation by hysterectomy, bilateral oophorectomy or bilateral salpingectomy but not tubal ligation.
9. Male patients should be willing to use barrier contraception ie, condoms until 6 months after the last study drug is taken.

10. Patients are willing and able to comply with the protocol for the duration of the study including undergoing treatment and scheduled visits and examinations.
11. **For inclusion in optional genetic research**, patients must provide separate informed consent. If a patient declines to consent to optional genetic research, this does not exclude the patient from participating in any aspect of the study.

### 3.2 Exclusion criteria

Patients should not enter the study if any of the following exclusion criteria are fulfilled:

1. Involvement in the planning and/or conduct of the study (applies to both AstraZeneca staff and/or staff at the study site)
2. Participation in another clinical study with an investigational product during the last 14 days (or a longer period, depending on the defined characteristics of the agents used).
3. Treatment with any of the following:
  - A 1st or 2nd generation EGFR-TKI (eg, afatinib, erlotinib or gefitinib) within 8 days or approximately 5 half-lives, whichever is the longer, of the first dose of study treatment (if sufficient wash-out time has not occurred due to schedule or PK properties, an alternative appropriate wash-out time based on known duration and time to reversibility of drug related AEs could be agreed upon by AstraZeneca and the Investigator).
  - Osimertinib in the present study (ie, dosing with osimertinib previously initiated in this study) or has previously received a 3rd generation EGFR-TKI (eg, CO-1686). Patients who were enrolled, screened but not dosed (ie, withdrew from the study prior to dosing) may be re-enrolled and rescreened if in the opinion of the Investigator, the reason(s) for earlier withdrawal no longer applies.
  - Any cytotoxic chemotherapy, investigational agents or other anticancer drugs from a previous treatment regimen or clinical study within 14 days of the first dose of study treatment.
  - Major surgery (excluding placement of vascular access) within 4 weeks of the first dose of study treatment.
  - Radiotherapy with a limited field of radiation for palliation within 1 week of the first dose of study treatment, with the exception of patients receiving radiation to more than 30% of the bone marrow, or with a wide field of radiation which must be completed within 4 weeks of the first dose of study treatment.

- Patients currently receiving (or unable to stop use at least 3 weeks prior to receiving the first dose of osimertinib) medications or herbal supplements known to be potent inducers of CYP3A4 or inducers/inhibitors of P-gp, as described in [Appendix G](#).
4. Any unresolved toxicities from prior therapy greater than Common Terminology Criteria for Adverse Events (CTCAE) Grade 1 at the time of starting study treatment; with the exception of alopecia and Grade 2 prior platinum-therapy related neuropathy.
  5. Spinal cord compression or brain metastases, unless asymptomatic, stable and not requiring steroids for at least 4 weeks prior to start of study treatment.
  6. Any evidence of severe or uncontrolled systemic diseases, including uncontrolled hypertension and active bleeding diatheses, which, in the Investigator's opinion, makes it undesirable for the patient to participate in the study or which would jeopardise compliance with the protocol, or active infection including hepatitis B, hepatitis C and human immunodeficiency virus (HIV). Screening for chronic conditions is not required.
  7. Any of the following cardiac criteria:
    - Mean resting corrected QT interval corrected for heart rate using Fridericia's correction factor (QTcF) >470 msec, obtained from 3 ECGs.
    - Any clinically important abnormalities in rhythm, conduction or morphology of resting ECG (eg, complete left bundle branch block, third degree heart block, second degree heart block, PR interval >250 msec)
    - Any factors that increase the risk of QTc prolongation or risk of arrhythmic events such as heart failure, hypokalaemia, congenital long QT syndrome, family history of long QT syndrome or unexplained sudden death under 40 years of age or any concomitant medication known to prolong the QT interval
  8. Past medical history of interstitial lung disease, drug-induced interstitial lung disease, radiation pneumonitis which required steroid treatment, or any evidence of clinically active interstitial lung disease.
  9. Inadequate bone marrow reserve or organ function as demonstrated by any of the following laboratory values:
    - Absolute neutrophil count (ANC)  $<1.5 \times 10^9/L$
    - Platelet count  $<100 \times 10^9/L$

- Haemoglobin <90 g/L
  - Alanine aminotransferase >2.5 times the upper limit of normal (ULN) if no demonstrable liver metastases or >5 times ULN in the presence of liver metastases
  - Aspartate aminotransferase >2.5 times ULN if no demonstrable liver metastases or >5 times ULN in the presence of liver metastases
  - Total bilirubin >1.5 times ULN if no liver metastases or >3 times ULN in the presence of liver metastases
  - Creatinine >1.5 times institutional ULN concurrent with creatinine clearance <50 mL/min (measured or calculated by Cockcroft-Gault formula); confirmation of creatinine clearance is only required when creatinine is >1.5 times institutional ULN.
10. Patients unable to swallow orally administered medication or patients with gastrointestinal disorders or significant gastrointestinal resection likely to interfere with the absorption of osimertinib and/or fexofenadine.
  11. History of hypersensitivity to active or inactive excipients of osimertinib or drugs with a similar chemical structure or class to osimertinib.
  12. History of hypersensitivity to active or inactive excipients of fexofenadine or drugs with a similar chemical structure or class to fexofenadine.
  13. Women who are breastfeeding.
  14. Judgement by the Investigator that the patient should not participate in the study if the patient is unlikely to comply with study procedures, restrictions and requirements.
  15. Any intake of grapefruit, grapefruit juice, Seville oranges, Seville orange marmalade, or other products containing grapefruit or Seville oranges within 7 days of the first administration of the IP until the final PK sample collection on Day 42 of the PK phase.

In addition, the following are considered criteria for exclusion from the exploratory genetic research:

18. Previous allogenic bone marrow transplant.
19. Non-leukocyte depleted whole blood transfusion within 120 days of the date of the genetic sample collection.

Procedures for withdrawal of incorrectly enrolled patients see Section [3.4](#).

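### Exclusion 3 reverses the washout for wide-field or extensive marrow radiotherapy: as written, finishing it days before the first dose does not exclude the patient (minor, wrong as written)

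*Protocol*

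**What the plan says.** Section 3.2 of the Protocol lists conditions that keep a patient out of the study. Exclusion 3 covers recent treatments. Its radiotherapy bullet begins "Radiotherapy with a limited field of radiation for palliation within 1 week of the first dose of study treatment, with the exception of patients", names as that exception patients whose radiation reaches more than 30% of the bone marrow, and continues "with a wide field of radiation which must be completed within 4 weeks of the first dose of study treatment".

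The neighbouring surgery bullet reads "Major surgery (excluding placement of vascular access) within 4 weeks of the first dose of study treatment". The last bullet of Exclusion 3, on CYP3A4 inducers and P-gp modulators, concerns patients "unable to stop use at least 3 weeks prior to receiving the first dose of osimertinib". Exclusion 5, on cord compression and brain metastases, applies "unless asymptomatic, stable and not requiring steroids for at least 4 weeks prior to start of study treatment".

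Sections 3 and 3.4 allow no exceptions to the eligibility criteria. Section 7.7 deals with radiotherapy while the patient is on study. No other section sets an interval between radiotherapy and the first dose.

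**The concern.** In a list of exclusions, an exception lets patients in. The bullet takes the more extensive radiotherapy out of the exclusion and attaches a condition that it be finished inside the last 4 weeks before dosing. The period that should bar the patient becomes the period in which completion is acceptable.

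What is at stake is eligibility and patient safety. Because the protocol permits no exceptions to its criteria, the text of the rule decides who may be dosed. A site that dosed a patient days after wide-field radiotherapy would not breach the written rule, so a check against the text would show no deviation. The primary analysis of the fexofenadine ratios is not affected.

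**Working it through.** There is no sample-size or power figure to reproduce. The check is a reading of the bullet against its neighbours, followed by simple day counts.

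**Inputs**
- Limited-field rule: 1 week (Section 3.2, Exclusion 3).
- Wide-field or more than 30% marrow: the 4-week figure in the same bullet.
- First dose of study treatment: taken as the fexofenadine dose on Day 1 of Treatment Period 1, because Section 4.1 starts the treatment period there.
- First osimertinib dose: 3 to 7 days after that fexofenadine dose (Section 7.2.1).
- Planned enrolment: 24 patients (Section 8.2).

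**Step 1: literal reading.** Three cases show what the bullet does.

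| Radiotherapy | Ends on | As written | Evident intent |
|---|---|---|---|
| Limited field, palliative | Day -3 | Excluded | Excluded |
| Wide field or >30% marrow | Day -3 | Not excluded | Excluded |
| Wide field or >30% marrow | Day -40 | Fails the completion condition | Not excluded |

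The second row is the safety gap. The third row shows the same reversal from the other side.

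**Step 2: what the neighbouring text supports.** The EGFR-TKI, chemotherapy and surgery bullets use a period before the first dose as the period in which treatment excludes. The surgery bullet uses the same 4 weeks. Heavier radiotherapy can only sensibly need longer than the 1 week set for limited fields. Together these point to at least 4 weeks clear. The list also contains unambiguous wording for such an interval, in the last bullet of Exclusion 3 and in Exclusion 5. The radiotherapy bullet does not use it.

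**Step 3: minimum gap to the first study dose (fexofenadine).**
- Wide field or >30% marrow, as written: 0 days.
- Limited field: 1 × 7 = 7 days.
- Wide field or >30% marrow, as intended: 4 × 7 = 28 days.
- Shortfall against the intent: 28 − 0 = 28 days. Shortfall against the limited-field rule: 7 − 0 = 7 days.

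**Step 4: minimum gap to the first osimertinib dose (add 3 to 7 days).**
- As written: 0 + 3 to 0 + 7 = 3 to 7 days.
- Limited field: 7 + 3 to 7 + 7 = 10 to 14 days.
- As intended: 28 + 3 to 28 + 7 = 31 to 35 days.

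**Step 5: scale.** The protocol gives no rate of such radiotherapy. Assuming, for illustration only, that 1% to 5% of patients completed it in the 4 weeks before dosing: 0.01 × 24 = 0.24 and 0.05 × 24 = 1.2, so 0.2 to 1.2 patients. This counts patients to whom the wording would matter. Harm would also require the site to follow the literal text and the patient to pass the other exclusions.

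**The case against.** The strongest reply is that the bullet is garbled and does not set a clear 0-day rule. Read literally it would also reject a patient who finished wide-field radiotherapy on Day -40, which is absurd. Wide-field radiation is also not a kind of limited-field radiation, so it cannot strictly be an exception to a limited-field rule. In context, the natural reading is 1 week for limited fields and 4 weeks for extensive ones, and most sites would apply that.

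There are also safeguards:
- Exclusion 4 covers "Any unresolved toxicities from prior therapy greater than Common Terminology Criteria for Adverse Events (CTCAE) Grade 1 at the time of starting study treatment".
- Exclusion 6 lets the investigator keep out patients with severe or uncontrolled systemic disease.
- Exclusion 8 covers "radiation pneumonitis which required steroid treatment, or any evidence of clinically active interstitial lung disease".
- Exclusion 9 covers "Inadequate bone marrow reserve or organ function as demonstrated by any of the following laboratory values", with floors for neutrophils, platelets and haemoglobin.
- Inclusion 4 requires radiological progression on the last treatment before enrolment. If radiotherapy counts as that treatment, which is arguable, a patient who has just finished it could hardly qualify.
- Table 1 repeats the eligibility check on Day -1 and Day 1. It schedules blood counts on Day -1, unless the patient was screened within 48 hours of Day 1, and again before the first osimertinib dose.
- Under Section 9.1 the sponsor's representative goes through the protocol with site staff before the first patient enters.
- Section 7.7 itself permits radiotherapy for painful bony metastases during the study.

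Much of this stands as a limit on the size of the problem. The intent is recoverable, and the number of patients concerned is small and unknown. It does not rescue the text. That the literal rule also fails a Day -40 completion confirms that it is wrong as written. The safeguards mostly act on abnormalities already present, and none sets a recovery interval. Repeating the eligibility check applies the same defective sentence again.

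**Conclusion.** The bullet is wrong as written, at minor severity. On its literal reading the minimum gap after the heavier radiotherapy is 0 days, which is 7 days shorter than for limited-field palliation and 28 days short of the evident intent. Counted to the first osimertinib dose, the gap is 3 to 7 days where 31 to 35 was meant.

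The defect in the wording is certain. The 28-day intent is an inference, though a strong one: the figure of 4 weeks stands in the bullet, the adjacent surgery bullet uses it as an excluded period, and only an interval longer than 1 week makes sense for more extensive radiation. The figure of 0.2 to 1.2 patients rests on an assumed rate and is for scale only.

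**What to change.** Split the bullet into two exclusions:

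- (a) limited-field palliative radiotherapy in the 1 week before the first dose of study treatment;
- (b) radiotherapy to more than 30% of the bone marrow, or with a wide field, that was not completed at least 4 weeks before the first dose of study treatment.

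The cost is a rewording of one bullet. Section 7.7 already records all treatment in the 4 weeks before study treatment, so no new data are needed. The downside is that any patient who would otherwise have been dosed under the literal text may wait up to 4 weeks longer.
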